## Appendix 2 New York Heart Association (NYHA) Classification

### NYHA Classification:

- I. Cardiac patients with no limitation in daily activity; ordinary physical activity will not lead to excessive fatigue, palpitations, dyspnea or angina.
- II. Cardiac patients with slight limitation in physical activity. Asymptomatic at rest, ordinary physical activity will cause excessive fatigue, palpitations, dyspnea or angina.
- III. Cardiac patients with obviously limitation in physical activity. Asymptomatic at rest, while less-than-ordinary activity cause excessive fatigue, palpitations, dyspnea or angina.
- IV. Cardiac patients who cannot stand for any physical activity. Symptoms of heart failure occurs even at rest, which is aggravated when undertaking physical activity.

### Appendix 3 Procedures for Mixed-Meal Tolerance Test (MMTT)

The MMTT is a standardized method to determine postprandial blood glucose levels. In this study, MMTT is used for assessing how HMS5552 affects postprandial blood glucose, insulin and C-peptide. (Note: All meals used for MMTT in this study are the instant noodle standard meal provided by the Sponsor).

Subjects are requested to avoid any heavy physical activities and high fat and high calorie food on the night prior before MMTT visit.

On the day of MMTT visit, subjects should be in fasting status (suggest no food and beverage intake from 22:00 at previous night until blood sampling is completed; water is allowed and fasting status should be kept for at least 8 hours).

Totally four MMTTs will be conducted for the whole study, including one at Visit 4 before study drug administration, and once each at Visits 7, 10 and 15 after study drug administration (except for MMTT at the timepoint 0).

Before the instant noodle standard meal, blood samples need to be collected at the timepoint 0 and then the instant noodles standard meal starts to be taken (timing starts from the first chewing of the noodles and the meal is finished within 10 minutes). Blood samples are collected at 30 minutes ( $\pm 3$  minutes are allowed) and 120 minutes ( $\pm 5$  minutes are allowed) after the instant noodles standard meal. When blood samples are being taken, food, water, and strenuous exercise is not allowed until all samples for MMTT are collected (30-minute blood sampling point is applicable to subjects enrolled after the protocol v1.1 taking effect).

If subjects withdraw from the study early and already discontinued study medications on the termination visit, then MMTT for the termination visit can be cancelled (other tests are the same as Visit 15).

#### Procedures for Taking the Instant Noodles Standard Meal

1. Adding seasoning. Take out the seasoning bag and add the seasoning to the noodles.
2. Cooking. Add approximately 550 ml boiling water (suggest to use immediately once the water is boiling) to the noodles. Cover the lid and start timing.
3. Stirring. After 2 to 2.5 minutes, open the lid and stir the noodles. Cover the lid again.
4. Noodles ready. Use chopsticks to stir the noodles well when they are cooked for 10 to 15 minutes.
5. Eating. Eat all the noodles within 10 minutes. The soup can be finished or left according to subjects' personal preference.

## Appendix 4 Procedures for SMBG

At Visit 2, blood glucose meters with matching blood collection needles and test strips are provided to all subjects. Subjects are instructed for SMBG. Subjects monitor fingertip blood glucose levels (fingertip blood glucose tests for FPG or PPG are required to be conducted at least twice a week; the frequency is increased when hypoglycemia is suspected. All test time and results are recorded in subject diaries) at appropriate frequency decided by the Investigator (based on the assessment on the risks of subjects' blood glucose concentration).

Throughout the entire study (Visit 2 to Visit 16), to give subjects safety guidance and assess the withdrawn criteria timely, the Investigator should ask subjects to contact research centers immediately if the results of fingertip plasma glucose test meet the following criteria:

1. Hypoglycemia. Visit 2 (-Week 4) to Visit 15 (Week 52), at any time, fingertip plasma glucose value  $\leq 3.9$  mmol/L.
2. Hyperglycemia.

Day 1 to before Week 12, fasting plasma glucose (central laboratory)  $\geq 13.3$  mmol/L.

Week 12 to before Week 24, fasting plasma glucose (central laboratory)  $\geq 11.1$  mmol/L.

Week 24 to Week 52, fasting plasma glucose (central laboratory)  $\geq 11.1$  mmol/L.

Blood glucose results are recorded by subjects in subject diaries. At each visit after Visit 2, subjects are required to take blood glucose meters and subject diaries to research centers for Investigator review.

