**4.5.2 Withdrawal due to Hyperglycemia**

Between Visits 2 and 15, subjects should carry out SMBG according to SMBG guidance (refer to Appendix 4 for procedures of SMBG). Subjects should contact the Investigator timely if plasma glucose exceed the value specified in SMBG guidance. Depending on the fingertip plasma glucose values, diet and exercise condition, the Investigator determines whether the subjects should return to study sites in advance for laboratory tests.

If a subject has a FPG value reaching the following criteria twice (at least once tested in the central laboratory) without any apparent causes at two consecutive visits, the Investigator will evaluate whether the subject will withdraw from the study with the reason recorded as hyperglycemia based on subject's actual situation.

1. Day 1–before Week 12: venous FPG (central laboratory)  $\geq 13.3$  mmol/L
2. Week 12–before Week 24: venous FPG (central laboratory)  $\geq 11.1$  mmol/L
3. Week 24–Week 52: venous FPG (central laboratory)  $\geq 11.1$  mmol/L.

If a subject is confirmed to withdraw from the study due to hyperglycemia, the subject must complete termination visit before withdrawal (refer to Section 4.6). Then, the study medications can be discontinued and routine diagnosis and treatment can be started.

The Investigator must ensure no other causes can be identified to explain poor glycemic control except for lack of efficacy (e.g., acute inflammations/infections, concomitant treatments, etc.). If the disease aggravation is unexpected progression, it should be reported as an AE.

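### Appendix 4 labels its three hyperglycemia contact values as central-laboratory results, so read literally no home fingertip test triggers the contact that Section 4.5.2 relies on; the effect is minor

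*Supplement*

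**What the plan says.** Appendix 4 (Procedures for SMBG) sets the rule for calling the site. Subjects are to "contact research centers immediately if the results of fingertip plasma glucose test meet the following criteria". Two kinds of criteria follow.

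- **Hypoglycemia:** "Visit 2 (-Week 4) to Visit 15 (Week 52), at any time, fingertip plasma glucose value" of 3.9 mmol/L or lower.
- **Hyperglycemia:** three lines. The first reads "Day 1 to before Week 12, fasting plasma glucose (central laboratory"), at 13.3 mmol/L or more. The second has the same form, for Week 12 to before Week 24, at 11.1 mmol/L or more. The third reads "Week 24 to Week 52, fasting plasma glucose (central laboratory"), also at 11.1 mmol/L or more.

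Section 4.5.2 (Withdrawal due to Hyperglycemia) depends on this guidance: "Subjects should contact the Investigator timely if plasma glucose exceed the value specified in SMBG guidance". The next step rests on home readings: "Depending on the fingertip plasma glucose values, diet and exercise condition, the Investigator determines whether the subjects should return to study sites in advance". The same section then lists its withdrawal limits, beginning "Day 1–before Week 12: venous FPG (central laboratory"), with the same three thresholds and periods as Appendix 4. It requires the limit to be reached twice, with at least one of the two results from the central laboratory.

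Appendix 4 also provides a check at visits: "subjects are required to take blood glucose meters and subject diaries to research centers for Investigator review".

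**The concern.** The lead-in to Appendix 4 names the fingertip test as the trigger, and the hypoglycemia line follows suit. The hyperglycemia lines name a different test, one that the subject cannot perform at home. Section 7.8 sends central-laboratory results to the study site, so the site would already hold any result that literally met one of these lines, and a call from the subject would add nothing.

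The rule has a purpose. Section 4.4.2 bars other antidiabetic drugs from the run-in onward, and Section 9.1 allows up to 188 subjects on placebo for 24 weeks. Contact between visits is the route by which a subject with high home glucose can be brought back early for laboratory tests. As written, that route has no number that a home reading can meet.

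**Working it through.** No figure in the plan needs reproducing. The check is a comparison of texts, followed by simple arithmetic on visit spacing.

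**Step 1. Which test does each part of protocol v1.1 name?**

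| Place | Test named | Value (mmol/L) |
|---|---|---|
| Appendix 4, lead-in | Fingertip | n/a |
| Appendix 4, hypoglycemia | Fingertip | ≤ 3.9 |
| Appendix 4, Day 1 to before Week 12 | Fasting, central laboratory | ≥ 13.3 |
| Appendix 4, Week 12 to before Week 24 | Fasting, central laboratory | ≥ 11.1 |
| Appendix 4, Week 24 to Week 52 | Fasting, central laboratory | ≥ 11.1 |
| 4.5.2, withdrawal, same three periods | Venous fasting, central laboratory | ≥ 13.3, 11.1, 11.1 |

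Appendix 4 has 1 + 3 = 4 contact values. One of the four names a fingertip result, and none of the three hyperglycemia values does.

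**Step 2. Is a home trigger for hyperglycemia given elsewhere?**

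- Section 4.5.2 gives none and points to the SMBG guidance.
- Section 7.7 points back to 4.5.2 and Appendix 4.
- Schedule note 17 asks for extra home tests and diary entries when hyperglycemia is suspected, but gives no number and no instruction to call.
- Visit 2 (Section 3.5.2) provides instruction on managing hyperglycemia, but refers to Appendices 4 and 8 for the details.
- Appendix 8 mentions a fasting value of 16.7 mmol/L, but as a limit for exercise, not for contacting the site.

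So the protocol contains no other fingertip contact value for hyperglycemia.

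**Step 3. How long could a recall be delayed?** If no call is made, the next scheduled visit supplies a laboratory fasting glucose. Visit days and windows come from the Schedule of Assessments and Section 3.5.

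- Double-blind period, Day 28 to Day 56: 56 − 28 = 28 days. At the extremes of the ±4-day windows: (56 + 4) − (28 − 4) = 36 days.
- After Week 28, Day 238 to Day 280: 280 − 238 = 42 days. At the extremes of the ±6-day windows: (280 + 6) − (238 − 6) = 54 days.

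The figures of 36 and 54 days are not ceilings. Section 6 and note c of the schedule allow holiday rescheduling without a protocol deviation, and Section 7.8 allows 72 hours for results to reach the site.

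**The case against.** **The intent is clear from the surrounding text.** The lead-in says the criteria apply to fingertip results. The contact sentence in 4.5.2 carries no laboratory qualifier, and the next sentence speaks of fingertip values. Only one of the two results needed for withdrawal must come from the central laboratory, so sites must already be ready to hold a value from another source against 13.3 or 11.1. This is probably what the sponsor meant, and many sites will read it so. It does not remove the contradiction: the same list says fingertip where a home value is meant, and puts the laboratory label on each of the three other lines. Sites may differ on when a subject should call.

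**Other safeguards exist.** Subjects are instructed at Visit 2 and again when SMBG records are reviewed. Note 17 asks for extra tests, the Investigator may act on any fingertip value, and laboratory fasting glucose is measured at every treatment visit. All of this stands, and it keeps the effect small. None of it supplies a numeric home trigger.

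**The correction does not cover everything.** Appendix 4 speaks of Visit 2 to Visit 16, yet its hyperglycemia values start at Day 1, and it has none for tests after meals. That is true. Whether values are wanted there is a clinical decision for the sponsor and does not bear on the mislabelled lines.

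**Conclusion.** The point holds as a wording fault in a safety instruction. Read literally, none of the three hyperglycemia contact values in Appendix 4 can be met by a home test, and Section 4.5.2 relies on them. The cost is a recall delayed by about one visit interval: nominally 28 days in the double-blind period and 42 days after Week 28, longer with windows or holiday rescheduling. This assumes that a site follows the label and that nothing else prompts a call. The documents give no basis for estimating how often that would happen.

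Three stronger readings are tempting but not supported.

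- **That hyperglycemia would go undetected.** Laboratory fasting glucose and review of diaries and meters continue at treatment visits, so the gap concerns escalation between visits only.
- **That the primary endpoint or the withdrawal rule is compromised.** HbA1c measurement, the 4.5.2 limits and the analyses do not depend on the contact value, and withdrawal never rests on a home value alone.
- **That a subject could pass through the study without a fasting home test.** Appendix 4 and note 17 do ask for fasting *or* postprandial tests, but Section 7.4 asks for fasting *and* postprandial and is equally in force. That difference is a separate consistency note.

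**What to change.** In the three hyperglycemia lines of Appendix 4, replace the central-laboratory wording with *fasting fingertip plasma glucose*. Keep 13.3, 11.1 and 11.1 mmol/L. Leave the central-laboratory withdrawal limits in 4.5.2 as they stand.

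Separately, for consistency only, change *or* to *and* for fasting and postprandial tests in Appendix 4 and schedule note 17 (reprinted in SAP 2.3.2), so that they match Section 7.4. The edit should not lower the frequency that 7.4 requires. That section can be read as at least two tests a week covering both kinds, or as each kind at least twice a week (2 + 2 = 4 tests). The sponsor should say which is meant before any number per kind is written in.

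The main change is one label on three lines. It needs no new data capture and alters no withdrawal criterion or analysis.

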**Appendix 5 Estimated Glomerular Filtration Rate Calculation****Calculation of eGFR with MDRD equation [16]**

1.  $eGFR = 175 \times [S_{cr}]^{-1.154} \times [Age (Year)]^{-0.203} \times [ \times 0.742 \text{ if female}]$

**Cr unit: mg/dL, Age unit: year**

2.  $eGFR = 175 \times [S_{cr} \times 0.01131]^{-1.154} \times [Age (Year)]^{-0.203} \times [ \times 0.742 \text{ if female}]$

**Cr unit:  $\mu$ mol/L, Age unit: year**

## Appendix 6 Rules for Managing Abnormal Liver Functions

The Investigator should be highly alert with increased liver biochemistry values during the study, and should ensure subjects' safety and assess the cause of abnormal liver function timely.

For abnormal liver biochemistry values occurring at different stages of the study, the below actions are suggested.

### Screening and Run-in Periods

1. Subjects with active liver disease are screen failures.
2. Subjects with ALT or AST  $> 2.5 \times \text{ULN}$  or total TBiL  $> 1.5 \times \text{ULN}$  are screen failures.
3. If a subject has ALT or AST values higher than the upper limit of normal range but are  $\leq 2.5 \times \text{ULN}$ , or TBiL higher than the upper limit of normal range but are  $\leq 1.5 \times \text{ULN}$ , the Investigator is suggested to find out the cause for abnormal liver function parameters (the Checklist for Collecting Abnormal Liver Function Information in the Investigator's folder can be used). Subjects can continue the subsequent study only when the Investigator can ensure the abnormal liver function will not affect the safety assessment or subjects' completion of the entire study or study procedures.

### Treatment Period

From Visit 4 to Visit 15 in this study

1. The Investigator can stop study medications based on subjects' actual condition if any of the following criteria is met (no need to wait for the retest results):
  - ALT or AST  $> 8 \times \text{ULN}$
  - ALT or AST  $> 5 \times \text{ULN}$  and lasts for  $\geq 14$  days
  - ALT or AST  $> 3 \times \text{ULN}$  and TBiL  $> 2 \times \text{ULN}$
  - ALT or AST  $> 3 \times \text{ULN}$  with liver damage symptoms (e.g., fatigue, nausea, vomiting, right upper abdominal pain or tenderness, fever, rash) or eosinophilia increase.

The Investigator should immediately provide active intervention or treatment to subjects and identify the cause. If necessary, consultation with hematologists is conducted. The Investigator should closely follow-up with the subjects until the liver function is recovered or returns to baseline status. The Investigator should record the relevant AEs or SAEs timely.

2. If subjects have ALT or AST  $> 3 \times \text{ULN}$  but do not meet withdrawal criteria, the Investigator must ask the subjects to come back to the research center and retake the liver function tests at the central laboratory within 48 hours after receiving the test report (local laboratory tests can

be done when necessary). The Investigator should record the relevant AE or SAE timely, and find out the cause for abnormal liver functions, and give necessary interventions. The Investigator should closely follow-up with the subjects until the liver function is recovered or returns to baseline status. The subjects can continue to receive treatment according to the visit schedule in the study protocol if the Investigator considers appropriate.

3. If subjects have ALT or AST higher than the upper limit of normal range but is $\leq 3\times$ ULN, the Investigator evaluates the clinical significance of the abnormal values (see Section 7.1.3 AEs Related to the Medical and Clinical Laboratory Examinations). If any AE criterion is met, an AE should be recorded. The Investigator needs to find out the cause for abnormal liver functions and give necessary interventions. The Investigator should closely follow-up with the subjects until the liver function is recovered or returns to baseline status. The subjects can continue to receive treatment according to the visit schedule in the study protocol if the Investigator considers appropriate.

## **Safety Observation Period**

All study drugs are stopped in the safety observation period. All new occurrence of clinically significant abnormal liver function at the last visit should be reported as an AE (refer to Section 7). The Investigator should give necessary interventions and follow-up with the subjects until the liver function is recovered or returns to baseline status.

## **Clarify the cause of abnormal liver function (for reference)**

The Investigator figures out causes of abnormal liver function based on subjects' actual medical situation or clinical experience. The Investigator can also refer to the following items for clarification (e.g. inquiry, physical examination or laboratory tests).

Medical history and related risk factors: e.g. short-term drinking history, drug abuse, acute drug overdose, blood transfusion history, unclean seafood intake, occupational toxic contact, exposure to jaundice or other high-risk population, familial liver disease history, etc..

Physical examination: if any hepatomegaly, jaundice and other symptoms/signs occur.

Concomitant medications: if any prescription or non-prescription drugs or herbs or health care products been used and may lead to liver injury before the occurrence of liver injury, e.g. acetaminophen, paracetamol, carbamazepine, chlorpromazine, chlorpropamide, steroid contraception drugs, erythromycin ethylsuccinate, non-urethane, halothane, ketoconazole, monoamine oxidase, nonsteroidal anti-inflammatory drugs, phenindione, phenylbutazone, phenytoin, sulfonamides and sodium valproate, etc..

Hematological examination results: e.g. prothrombin time (PT), hepatitis A, B, C, D, E virus related tests, anti-cytomegalovirus antibodies, EB virus antibodies, anti-smooth muscle antibodies, anti-mitochondria antibodies, anti-neutrophil cytoplasmic antibodies, etc.

Other tests: e.g. abdominal ultrasound, CT or MRI if needed.

If necessary, hepatologists are consulted.

## Appendix 7 Recommendations for Managing Hypoglycemia

(for reference)

1. When suspected hypoglycemia symptoms appear (e.g. palpitation, anxiety, sweating, hunger etc, or altered mental status, cognitive impairment, convulsion, coma, etc.), blood glucose level should be measured immediately for a concise diagnosis. If blood glucose is difficult to measure, treatment for hypoglycemia is given temporarily.
2. Treatment for new occurrence of hypoglycemia
  - 1) Subject with clear consciousness. Take glucose or sugary food as soon as possible (suggest to take 15 to 20 grams of sugary food orally, glucose is preferred).  
**Caution:** to avoid a delay in the sugar absorption, don't eat any foods immediately after taking sugars described above.
  - 2) Subject with no consciousness or coma. Call 120 and send the subject to hospital immediately. Don't put food, liquid, or hand into the subject's mouth. Keep the subject's airway open. Recommended treatment: intravenous injection of 20 to 40 mL 50% glucose solution or intramuscular injection of 0.5 to 1.0 mg glucagon.  
After the treatments mentioned above, blood glucose level is monitored every 15 minutes.
  - 1) If plasma glucose level is still  $\leq 3.9$  mmol/L, oral intake of sugary food or glucose injection will be done once again.
  - 2) If plasma glucose level is  $> 3.9$  mmol/L but the time to next meal is more than 1 hour, food consists of starch or protein will be given after 10 to 15 minutes.
  - 3) If plasma glucose level is still  $\leq 3.0$  mmol/L, intravenous injection of 60 mL 50% glucose solution will be given.
  3. Once hypoglycemia has been corrected
    - 1) Find out the cause for hypoglycemia and adjust the drug administration. For subjects with impaired consciousness, plasma glucose level in short-term does not need to be strictly controlled.
    - 2) Pay attention to cardiovascular diseases induced by hypoglycemia.
    - 3) Frequent SMBG is suggested.
    - 4) Increase diabetic education and carry diabetes emergency cards.

If hypoglycemia has not been corrected,

- 1) Intravenous injection of 5 or 10% glucose, or combined with glucocorticoid.
- 2) Monitor blood glucose for at least for 24 to 48 hours after recovery of consciousness.

## Appendix 8 Medical Nutrition Therapy for T2DM

(Chinese Guideline for the Prevention and Treatment of T2DM (2013 Edition), Chinese Diabetes Society)

Medical nutrition therapy is a special intervention approach in treating the nutritional problems in patients with diabetes mellitus, including personalized nutrition assessment, nutrition diagnosis, relevant nutritional intervention plan to be implemented and monitored in a certain period of time. Medical nutrition therapy is important in the prevention, treatment, self-management, and education for diabetes mellitus and relevant complications. By modifying nutrient structure, medical nutrition therapy is beneficial in blood glucose control and helps to maintain optimal body weight and prevent malnutrition.

### General principles for nutrition therapy

Subjects with diabetes mellitus and prediabetes need to receive personalized medical nutrient treatment under the guidance of a registered dietitian who is familiar with diabetes treatment or an integrated management team (including diabetes educators). After nutrition condition of the patient is assessed, a reasonable target should be set for controlling the total energy intake, maintaining appropriate and balanced distribution of various nutrients, and achieving metabolic control goal. Personal food preferences are satisfied as much as possible. Moderate body weight loss, which can be maintained by physical exercises and behavior changes, is recommended for overweight or obese patients.

